 - MAIA-Y (how well young people notice, understand, and respond to their body's internal signals of emotions, breathing, and physical sensations)

- DERS-16 (difficulties in emotion regulation scale)
- TASC-R (therapeutic alliance scale for children)
- PHQ-9, GAD-7, and PSS-4 (measures of symptoms of depression, anxiety, and stress)
- KidCOPE (pediatric coping strategies)

Intervention Activities

- Participating juveniles will use the Healpod, a sensory intervention booth, prior to their 1 to 2 weekly scheduled therapy sessions.
- Each session will involve:
 - 5 minutes of guided sound, music, gentle vibration, and soft light therapy in the Healpod
 - 5 minutes of immediate expressive writing/ journaling or drawing to capture emotional reflections
 - Meeting with their therapist right after each Heal session and after expressive writing/journaling or drawing
 - Post-Heal Therapy Assessment filled out by the therapist.
- The Heal sessions are designed to promote emotional regulation and provide a non-verbal pathway into improving outcomes of traditional therapy.

Therapy Integration

- Expressive writing/journaling or drawing output from each session will serve as a bridge into CBT/DBT talk sessions with therapists.
- Therapists will document observations of engagement, regulation, and openness in the Heal Therapist Assessment form.

Follow-Up Assessments

- Bi-weekly reassessments using forms PHQ-9, GAD-7, PSS-4
- Monthly reassessments using forms of MAIA-Y, DERS-16, TASC-R, kidCOPE

Data Collection and Confidentiality

- Data sources include standardized scales, session journals, and therapist assessments.
- For confidentiality, identifiable information will be separated from research data; participants will be coded with unique study IDs.

End-of Study-Activities

- Upon completion of the 8-week study period, participants will complete a final evaluation.

- Participating juveniles and their parents/guardians or LARs will be informed of study completion, with results summarized in age-appropriate language.
- Data will be securely archived in compliance with IRB and HIPAA requirements.

Duration

8 Weeks

MAIN PROTOCOL

Introduction

Background of the Problem: Epidemiology, Prevalence/Incidence

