- TASC-R (Baseline + Midpoint + End).
- Structured journaling, therapist observations and validated scales with PHQ-9, GAD-7, and PSS-4 (every 2 weeks) will assess changes in coping strategies and mental health symptoms of depression, anxiety, and stress.
- Exploratory objectives will be addressed through qualitative analysis of journals and the feedback from therapists (by session) where applicable.
- Cognitive and behavioral coping will be evaluated with the standardized KidCOPE assessment tool (Baseline + Midpoint + End).

Key Design Features

- **Single-arm, open-label:** All participants will receive the intervention; no placebo or control group will be used.
- **Pre-post comparisons:** Each participant will serve as their own control, minimizing between-subject variability.
- **Setting:** The trial will be conducted at San Luis Obispo (SLO) County Juvenile Hall. All interventions will occur on-site.
- **Duration:** Each participant will be enrolled for 8 weeks, completing up to 16 Heal sessions plus baseline, bi-weekly, midpoint, and endpoint assessments.
- **Sample Size:** The study will enroll up to 8 participants (male and female youth ages 12-18).
- **Therapist involvement:** Facility therapists and/or probation staff will administer assessments and conduct post-session discussions to support integration of the intervention into therapy and be available for any AE support.

Rationale for Design

A randomized controlled trial (RCT) is not feasible in this setting due to the small population size of up to 18 juveniles in the SLO County Juvenile Hall. The pre-post design provides practical feasibility while still generating meaningful quantitative and qualitative data on changes in emotional regulation, therapeutic alliance, mental health outcomes, and coping. Findings from this pilot will inform the feasibility and effect sizes needed to plan a larger, fully powered RCT in the future.

Also, tracking emotional regulation not only with a dysregulation scale (e.g., DERS-16) but also with a mechanism-focused measure like MAIA will help us see if youths' body awareness/self-regulation improves. This lets us see *how* the Heal intervention might work, not just *if* it works.

Schedule of Assessments

Standardized Test	Start 0	Wk 1	Wk 2	Wk 3	Wk 4	Wk 5	Wk 6	Wk 7	Wk 8	
Mini-IPIP-A (Adolescent)	X									
MAIA-Y (Youth)	X				X					X
DERS-16	X				X					X
TASC-R	X				X					X
PHQ9	X		X		X		X			X
GAD7	X		X		X		X			X
PSS4	X		X		X		X			X
KidCope	X				X					X

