document or script approved by the IRB. Prospective participant will not be enrolled when the person obtaining informed consent is unwilling to listen to or consider the information, even if the person providing informed consent agrees to be in the research. The informed consent process will continue throughout participation in the study, and consent will be informally verified on a continuing basis and recorded in the probation and clinical staff notes on an on-going basis. As a part of the on-going consent, significant new information will be given to the participant, and continuing consent will be documented as an addendum to probation and clinical staff notes with the PI being timely notified.

Screening and Enrollment

Screening will include review of inclusion and exclusion criteria such as age, custody status, length of stay, assent capacity, parental/guardian or LAR permission, language, and clinical stability and participation in the SLO County Juvenile Hall.

Study Visits

Because participants are housed in SLO County Juvenile Hall facility, all interactions will take place on-site. JIY will participate in baseline assessments at enrollment, followed by structured Heal intervention sessions for 8 weeks. Assessments (questionnaires, scales, journaling) will be repeated at 2-week intervals and at study completion. Session journals will be completed after each session inside the Healpod.

Standardized assessment will be completed as follows: Mini-IPIP-A (At the start), MAIA-Y (Baseline + midpoint + End), DERS-16 (Baseline + midpoint + End), TASC-R (Baseline + midpoint + End), PHQ-9 (every 2 weeks), GAD-7 (every 2 weeks) and PSS-4 (every 2 weeks) and KidCOPE (Baseline + midpoint + End). Each "visit" will consist of: (1) HealPod session (~5 minutes), (2) journaling (~5 minutes), and (3) therapy session with a therapist (~15 to 30 minutes).

Interventions

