- Although the HealPod presents minimal physical risk, the study excludes pregnant participants out of an abundance of caution. While there is no evidence of harm,

the physiological and emotional sensitivity associated with pregnancy warrants exclusion to ensure participant safety.

The HealPod meets all criteria for a Non-Significant Risk device under **21 CFR §812.3(m)**. This study will therefore proceed under the abbreviated IDE requirements for NSR behavioral research and does not require an FDA IDE submission.

- **Drug/Biologics**

NA

- **Food**

NA

- **Cosmetics**

NA

- **Tobacco**

NA

- **Others: Behavioral Research**

Intervention

The Heal study intervention is a carefully designed program aimed at promoting emotional regulation, improved therapeutic alliance, better mental health outcomes and adaptive coping skills among JIY. This program is based on principles from affect regulation theory, mindfulness-based interventions, and sensory modulation approaches, which emphasize the role of both bottom-up physiological regulation and top-down reflective processing. By addressing both bottom-up physiological regulation (through sound, music, and gentle vibrations) and top-down reflective processing (through expressive writing/journaling or drawing), the intervention aims to reduce emotional dysregulation and prepare youth for more effective alignment with therapy.

Components

The Heal intervention program consists of several key components:

- **Sensory intervention:** Participants sit inside the Healpod, a 4- by 6-foot enclosed booth equipped with speakers, bass shaker, ambient light, calming sound, and music for ~5 minutes per session.

- **Expressive writing/ journaling or drawing:** Immediately following the Healpod session, participants spend ~5 minutes journaling or drawing about their experience, emotions, and/or reflections.
- **Therapeutic integration:** Participating juveniles then meet with a clinician for a brief, standard therapy interaction of approximately 15 to 30 minutes, using their Heal session journal as a bridge into deeper therapeutic discussion.

The intervention will be delivered in an individual, in-person format within the the SLO County Juvenile Hall setting. Sessions will occur once or twice weekly over an 8-week period, for up to 16 sessions per participant. Sessions will be supervised by trained facility staff with oversight by licensed clinicians.

Implementation

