- **Parental/guardian or LAR consent:** Parents or legal guardians will be contacted to provide informed consent prior to enrollment. If they are not able to consent in English they will be provided a Spanish translated Consent form.

Consent/assent forms will clearly state that participation is voluntary, that declining will not affect privileges or probation status, and that participants may withdraw at any time.

Participation in this study will have no effect on probation status, case outcomes, or parole decisions. Parole boards and probation staff will not receive information regarding a youth's participation in the study.

Deception

No deception is involved in this study. All participants and guardians will receive full information regarding the study's objectives, procedures, risks, and benefits.

Study Population

Inclusion Criteria

Participants must meet all of the following criteria to be eligible for enrollment:

- **Age:** Youth aged 12-18 years at the time of enrollment
- **Custody:** Currently detained in SLO County Juvenile Hall
- **Diagnosis/clinical characteristics:** Documented history of either being at risk or having a history of or currently diagnosed with a mental health disorder (e.g., stress, depression, anxiety, ADHD, PTSD) and/or SUD, as identified in clinical or probation records
- **Length of stay:** Facility records must project a remaining stay of at least 8 weeks at the time of enrollment.
- **Language/comprehension:** Ability to understand and follow study instructions in English at a basic level. Youth with limited literacy will be allowed to complete journaling through drawings or assisted prompts.

- **Capacity to assent (21 CFR 50.55):** All JIY are between ages 12-18, an age range in which youth are generally capable of providing meaningful assent. The IRB will be provided with (1) a youth-friendly assent script, (2) a description of who will obtain assent (clinical staff), and (3) assurances that assent will be voluntary, with no consequences for refusal or withdrawal. On-site clinical staff will confirm each youth is medically and psychiatrically stable enough to understand and participate in the assent process.
- **Consent/assent:** Youths must provide verbal assent after the study has been explained in age-appropriate language. A parent, legal guardian, or LAR must provide written informed consent.

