Clinical stability: On-site clinical staff must confirm the juvenile is medically and psychiatrically stable enough to participate in the planned activities.
Willingness to participate: Youths must agree to comply with intervention procedures, including sitting in the Healpod, completing journaling or drawing after sessions, and completing study questionnaires.
- **Concurrent treatment:** Youth receiving standard counseling or prescribed psychotropic medication remain eligible for their normal ongoing treatment.

Vulnerable Populations

- **Inclusion of children:** Because participants are minors, parental/guardian or LAR consent is required in addition to participant assent. All study materials will be presented in age-appropriate language.
- **Inclusion of detained (prisoner) youth:** Individuals who are incarcerated or detained are eligible for this study. Given their custodial status, additional safeguards will be in place to minimize risk of coercion or undue influence:
- **Voluntariness:** Participation is voluntary. Refusal or withdrawal will not affect probation status, privileges, release dates, or case outcomes. “The minor advantages of participation (e.g., opportunity for relaxation, time for journaling, positive interaction with staff) are not of such magnitude that they would impair the youth’s ability to weigh risks and benefits or unduly influence their decision to participate.
- **Independent consent/assent:** Assent will be obtained by trained staff who are not in positions of custodial or disciplinary authority (e.g., not probation officers or detention guards). Youths will be given time to ask questions in private.
- **Age-appropriate materials:** Information sheets and assent scripts will be written in plain, adolescent-friendly language. Translations and verbal explanations will be provided as needed.
- **Parental/Gardian or LAR consent:** Written consent will be obtained from a parent, guardian, or LAR in addition to youth assent.
- **Confidentiality:** All data will be de-identified, stored securely on HIPAA-compliant servers, and not shared with probation or courts.

Regulatory and Ethical Safeguards

The study will adhere to ethical principles and comply with federal regulations governing research with vulnerable populations.

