- **Therapy integration:** ~15 to 30 minutes of discussion with a clinician using the journal as a foundation/bridge

Follow-up Assessments: For the follow-up assessments of the primary endpoint, emotional regulation, we will employ MAIA-Y(Midpoint + End) and DERS-16 (Midpoint + End). For the secondary endpoints we will use TASC-R (Midpoint + End), PHQ-9 (every 2 weeks), GAD-7 (every 2 weeks) and PSS-4 (every 2 weeks). Additionally, the study will incorporate structured session journals with each session, and therapist assessments with each session where applicable. For the exploratory objectives, we will administer kidCOPE at Midpoint and end. Additional assessments will be done through qualitative analyses of journals and the feedback from therapists, session-based where applicable.

Final assessments will be completed at week 8.

Data Collection: Data will include self-report scales, therapist observations, and expressive writing/journaling or drawing content (de-identified before analysis). All data will be stored securely in compliance with HIPAA.

Research Arms or Groups of Interventions

Intervention Arm (Single-Arm Study): All eligible youth who provide assent and whose parent/guardian provides consent will receive the Heal intervention in addition to standard facility care.

Comparator: There is no separate control group. Outcomes will be assessed by comparing participants' post-intervention results to their own baseline measures.

Standard of Care: Routine counseling, group sessions, other treatments and education provided by the facility continue unchanged.

Control Group: There is no separate control group; each participant serves as their own control through pre-post comparisons.

Study Procedures and Timeline

Mini-IPIP-A (at the start), MAIA-Y(Baseline + Midpoint + End), DERS-16(Baseline + Midpoint + End), TASC-R (Baseline + Midpoint + End), PHQ-9 (every 2 weeks), GAD-7 (every 2 weeks) and PSS-4 (every 2 weeks), and KidCOPE (Baseline + Midpoint + End).

- **Baseline (Day 0-7 after consent)**

- **Mini-IPIP-A:** An adolescent-friendly questionnaire that quickly measures the Big Five personality traits (Extroversion, Agreeableness, Conscientiousness, Neuroticism, and Openness)
- **MAIA-Y:** measures how well JIY notice, understand, and respond to their body's internal signals such as emotions, breathing, and physical sensations to support emotional awareness and self-regulation.

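### The protocol permits probation staff to administer the scales and lead post-session discussions, which conflicts with its confidentiality assurances whenever they do so

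*Protocol*

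**What the plan says.** The bullet on therapist involvement in the protocol's Key Design Features reads: "Facility therapists and/or probation staff will administer assessments and conduct post-session discussions". The same sentence adds support for adverse events and gives integration of the intervention into therapy as the purpose.

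Two assurances bear on this:

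- Consent and Assent Process: "Parole boards and probation staff will not receive information regarding a youth's participation in the study".
- Vulnerable Populations, Confidentiality: "All data will be de-identified, stored securely on HIPAA-compliant servers, and not shared with probation or courts".

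Elsewhere the meeting after a Heal session belongs to a therapist or clinician:

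- Summary, Intervention Activities: "Meeting with their therapist right after each Heal session".
- Study Visits: the third part of each visit is a therapy session with a therapist.
- Components, Therapeutic integration: "Participating juveniles then meet with a clinician for a brief, standard therapy interaction".
- Study Interventions/Activities, Intervention Delivery: "discussion with a clinician using the journal as a foundation/bridge".
- Subpart C, Prisoner Protections: the therapist meeting after every session is cited as mitigating risk.

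On the data, the Data Collection paragraph under Study Interventions/Activities states: "Data will include self-report scales, therapist observations, and expressive writing/journaling or drawing content". The Data Collection section under Interactions with Participants describes DERS-16, MAIA-Y, TASC-R, PHQ-9, GAD-7, PSS-4 and KidCOPE as self-report. Study Procedures and Timeline allows DERS-16, PHQ-9, GAD-7, PSS-4 and KidCOPE to be read aloud where literacy is limited. Primary Analyses makes the DERS-16 change from Baseline to Week 8 the primary analysis.

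**The concern.** Two things are at stake.

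The first is the assurance to detained minors and their guardians. The protocol itself treats probation officers as holders of custodial authority: under Vulnerable Populations it gives them as an example of staff who may not obtain assent. Key Design Features then admits the same group to data collection and to the discussion built on the youth's journal.

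The second is measurement. A youth may answer questions about anger, distress or control differently when a probation officer asks them. The study is open-label with no control group, so an administrator effect that differs between Baseline and Week 8 would enter the change score with nothing to reveal it. An effect equal at both times would cancel from the change. Willingness to talk in the post-session discussion is also listed as evidence for the therapeutic alliance objective, so the choice of discussion leader bears on a secondary outcome too. Under Sample Size Rationale, the resulting effect sizes and variances are meant to guide the power calculation of a later trial.

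**Working it through.** No figure in the protocol is in dispute, so the check compares the texts.

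**1. What Key Design Features allows.** The and/or wording is satisfied by therapists alone, by both groups, or by probation staff alone. Only the last two raise the conflict.

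**2. Against the Consent and Assent Process section.** That assurance concerns information about participation and carries no condition. Someone who gives a youth a study scale or leads the discussion after a Heal session knows that the youth takes part. When probation staff do this work, both texts cannot be followed.

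**3. Against the Confidentiality bullet.** This concerns data, so the conflict depends on what probation staff hear or see.
- Scales: a form completed and returned unseen need not disclose answers; a read-aloud scale may.
- Discussion: it is built on the journal, and journal content is listed as study data. A probation officer leading it would hear or see study data.

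**4. Against the descriptions of the post-session meeting.** All five places listed above name a therapist or clinician; none names probation staff. The discussion in Key Design Features could be a separate event, but that reading is weak. Its stated purpose is integration into therapy, Intervention Delivery puts the clinician discussion under that same label, and no other discussion is described.

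**5. Whether narrower assurances remove the conflict.** Confidentiality Protections bars only sharing that could affect case decisions. The parole board paragraph in Subpart C bars only considering participation in such decisions. Neither cancels the broader statement that probation staff receive no information.

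**6. Other probation roles that do not fit the absolute assurance:**
- supervision of sessions (Introduction; Study Definition);
- ongoing consent recorded in probation notes (Consenting);
- the exit interview involving probation or clinical staff (Study Procedures and Timeline);
- help with recruitment (Subpart C);
- assessment of pressure and understanding during consent (Traditional Consent Process);
- introduction of the study (Electronic Consent Process).

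The roles in recruitment and in introducing the study also sit badly with two other statements. The section on juvenile prisoners reserves recruitment, assent and consent for people outside disciplinary and release decisions. HIPAA Waivers gives recruitment to behavioral health staff only.

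**7. Workload if therapists or behavioral-health staff give every scale.** The Schedule of Assessments has occasions at weeks 0, 2, 4, 6 and 8, so five per youth. Key Design Features gives up to 8 participants; the Statistical Analysis section gives no more than 18.
- 5 × 8 = 40 occasions
- 5 × 18 = 90 occasions

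**The case against.** The strongest reply is that the sentence permits and does not prescribe. It sits under a heading about therapists and merges three duties, one of which, support in distress, the Emergency protocols bullet properly shares with probation officers. It may simply be loose drafting. This stands in part: a reader might infer that staff who follow Key Design Features necessarily break the assurance, and the text does not support that. Using therapists alone breaks nothing. The conflict arises only when the probation option is used.

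A second reply is that the assurance is the faulty text. The sentence before it concerns probation status and parole decisions, and it could be read as barring information only to case decision-makers. Read literally, it already fails because of the other probation roles. This also stands in part: editing Key Design Features alone will not resolve matters. It does not excuse that section, because the assurance as written bars receipt of information and the Confidentiality bullet separately bars sharing data with probation.

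Two stronger inferences should not be drawn. One is that the therapist being rated will collect TASC-R and see the answers; the protocol does not say so. The other is a numerical bias in the DERS-16 change. The protocol does not say which staff will act at which visit, and it gives no basis for the size of any effect.

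**Conclusion.** The point holds as a conditional contradiction that should be corrected. Key Design Features permits what the Consent and Assent Process section rules out. Where answers or journal content are heard or seen, it also permits what the Confidentiality bullet rules out. It departs from five consistent descriptions of a therapist- or clinician-led meeting, one of which serves as a prisoner-protection safeguard.

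The statistical consequence is a possible bias in self-reported change, of unknown size and direction. It depends on probation staff actually being used and on their effect differing between Baseline and Week 8. The conclusion rests on reading the post-session discussion as the therapy meeting described elsewhere. It also assumes that no document outside this protocol, such as the intervention manual mentioned under Implementation, already restricts who gives the scales.

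**What to change.** In Key Design Features, remove probation staff from administering assessments and conducting post-session discussions, and keep their availability in case of distress as under Emergency protocols. State that therapists or behavioral-health staff without custodial authority give the scales, with the same administrator type for each youth at Baseline and Week 8. If the intervention manual already settles this, refer to it.

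Reconcile the absolute assurance in Consent and Assent Process with the probation roles in the Introduction, Study Definition, Consenting, Study Procedures and Timeline, Subpart C, Traditional Consent Process and Electronic Consent Process. How that assurance is reworded is for the sponsor and the IRB. Separately, reconcile the probation roles in recruitment and in introducing the study with the section on juvenile prisoners and with HIPAA Waivers.

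The cost is wording plus minor scheduling of the assessment occasions counted above. Therapists and behavioral-health staff are already named in the protocol, but it does not say how many are available.

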To ensure consistency and fidelity, a detailed intervention manual will guide all sessions. Staff will undergo protocol-specific training prior to implementation. Adherence will be monitored through session logs, therapist checklists, and participant feedback. All journaling will be de-identified before analysis to protect confidentiality of the JIY.

Accepted Variances

While the intervention is standardized, opportunities for individual tailoring are built in. For example, participating juveniles may select from a set of calming sound tracks, choose whether to sit with the curtain open or closed, or opt to journal through drawing rather than writing. Session length may be shortened if a participant experiences discomfort, and journaling prompts may be adjusted for literacy levels. These adaptations ensure that the intervention remains accessible and effective for diverse participants with varying needs. Some participating juveniles may be read the questions from the standardized questions and may be given details on what the questions are asking if their comprehension skills or reading skills are low.

Naive Condition

This pilot does not include a separate control group. Participants serve as their own controls, with pre-intervention baseline measures compared to post-intervention outcomes. Usual care, such as counseling, behavioral groups, and other programming, will continue in parallel, ensuring no participant is deprived of standard services. The absence of a control group reflects the small population size, ethical considerations, and the feasibility goals of this pilot, while still allowing for meaningful within-subject evaluation of intervention effects.

Confidentiality Protections

All data will be de-identified at the point of collection. Journals will be labeled only with study ID numbers and stored separately from identifying information. Electronic data will be stored in password-protected, HIPAA-compliant systems accessible only to authorized

study personnel. No individual-level data will be shared with probation or facility staff in ways that could affect case decisions.

Consent and Assent Process

Because participants are minors in custody, a two-step process will be followed:

- **Youth assent:** Each participant will be given age-appropriate information and asked for verbal voluntary assent.

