- **Parole board protections:** Adequate assurance has been established that participation in this research will not be considered by parole boards, probation officers, or other decision-making authorities when determining parole status, probation terms, or release dates. Participation or non-participation in the study will have no influence on legal outcomes, and this assurance will be communicated to both participants and their guardians during the consent/assent process.

Subpart D: Children and Minors in Research

Because participants are minors under 18, Subpart D applies. To ensure compliance with these regulations, this study is structured as follows:

- Parental/guardian/LAR consent will be obtained along with youth assent in age-appropriate language.
- The study involves minimal risk and offers a direct prospect of benefit through improved emotional regulation, improved therapeutic alliance, better mental health and improved coping skills.
- Youths with limited literacy will be supported by means of such assistance as non-guided/sounds-only sessions, journaling by drawing, and assisted prompts.
- Consent/assent documents will explicitly affirm the right to withdraw at any time without penalty.

Statistical Analysis

Study Purpose and Analytic Frame

This proposed research is a pilot, single-arm, pre-post interventional study with an expected enrollment of no more than 18 JIY detained in SLO County Juvenile Hall. The primary aim is to assess feasibility, safety, and preliminary signals of efficacy for the Heal intervention. Given the small sample size, analyses will emphasize within-person change estimates, effect sizes with confidence intervals, and graphical trajectories, rather than

confirmatory hypothesis testing. The data will provide estimates to inform a subsequent larger and adequately powered trial.

Variables and Endpoints

- **Primary outcome:** Emotional regulation, measured by the MAIA-Y, DERS-16 at baseline, mid-study, and study completion along with self-reported session journals.
- **Secondary outcomes:** Therapeutic alliance (TASC-R) measured at baseline, mid-point and end, and therapist assessment session journals. Mental health outcomes of depression (PHQ-9), anxiety (GAD-7), stress (PSS-4) measured every 2 weeks.
- **Exploratory outcomes:** Coping skills (KidCOPE) measured at baseline, mid-point and end, and study feasibility. Safety profile outcomes of AEs and SAEs.
-

Sample Size Rationale

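### Continuing consent is to be recorded in probation staff notes, although the protocol promises that probation staff will not be told about a youth's participation

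*Protocol*

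**What the plan says.** The Consenting text under Interactions with Participants describes consent as a process that runs through the study. It says that "consent will be informally verified on a continuing basis and recorded in the probation and clinical staff notes on an on-going basis". Where significant new information is given, "continuing consent will be documented as an addendum to probation and clinical staff notes with the PI being timely notified".

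Four other statements bear on what probation learns or may do:

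- Consent and Assent Process: "Parole boards and probation staff will not receive information regarding" a youth's participation. The sentence has no qualifier.
- Confidentiality Protections: "No individual-level data will be shared with probation or facility staff in ways that could affect case decisions".
- Subpart C: Prisoner Protections, on parole boards: "participation in this research will not be considered by parole boards, probation officers, or other decision-making authorities" when parole status, probation terms or release dates are decided.
- Vulnerable Populations, Confidentiality: data are de-identified, "stored securely on HIPAA-compliant servers, and not shared with probation or courts".

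Probation staff also have study roles. Under Key Design Features, "Facility therapists and/or probation staff will administer assessments and conduct post-session discussions". Other sections give them supervision, oversight, exit-interview, recruitment and consent tasks.

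**The concern.** The participants are detained minors, and the protocol places the study under Subpart C. Voluntariness therefore leans heavily on the assurances given at assent and consent. If one of them is that probation will not know who takes part, while another section has probation staff notes carry each youth's continuing consent, the youth and the parent decide on a false statement.

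There is a second, less certain consequence. If a wish to stop would be visible in notes kept by the authority that supervises the youth, some may stay in who would otherwise leave. That would bear on voluntariness first, and on how retention is read second.

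**Working it through.** No arithmetic applies. The check is whether the statements can all be followed at once.

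**Step 1. What the note contains.** An entry that consent has been verified tells its reader that the youth is in the study and was still willing on that date. The phrase may mean a probation file or the working notes of on-site probation staff. On either reading, probation staff hold the information.

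**Step 2. The note against each assurance.**

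| Section | What is promised | Compatible with consent entries in probation notes? |
|---|---|---|
| Consent and Assent Process | Probation staff do not receive information on participation | No: it bars receipt |
| Confidentiality Protections | No sharing in ways that could affect case decisions | Yes: it limits effect |
| Subpart C, parole boards | Participation not considered in decisions | Yes: it limits use |
| Vulnerable Populations, Confidentiality | De-identified data not shared with probation or courts | Arguable: it concerns study data, not consent status |
| Study Definition, identifiable information | Identifiable records stay with the Behavioral Health Team | Poor fit if the entry names the youth |
| Data Security, access control | Only clinicians and study staff see identifiable information | Poor fit on the same condition |

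The firm contradiction is with the first row. No section reconciles the two.

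**Step 3. Whether removing the notes would make the promise true.** It would not. Probation staff would still learn who takes part through these roles:

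- supervising sessions (Introduction);
- on-site oversight (Study Definition);
- administering assessments, as an alternative or in addition to therapists (Key Design Features);
- the exit interview, as an alternative to clinical staff (Study Procedures and Timeline);
- helping with recruitment (Subpart C);
- judging understanding and undue influence during consent (Traditional Consent Process);
- introducing the study electronically (Electronic Consent Process).

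The last five sections also name therapists, clinicians or clinical staff, so an alternative is already written in.

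**Step 4. Whether the notes reach the outcomes.** They record consent. Nothing in the Consenting text puts a DERS-16, PHQ-9 or GAD-7 answer into them. No path from the notes to the scale scores is stated.

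**Step 5. Reach.** The instruction covers all participants. Key Design Features gives up to 8 and Statistical Analysis no more than 18. Participation lasts 8 weeks. Study Procedures and Timeline adds checks of willingness to continue around Weeks 2, 4 and 6, but does not say that their results go into these notes.

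**The case against.** The best defence is that the protocol protects youths against consequences, and does so repeatedly: refusal or withdrawal is not to affect probation status or privileges, and participation is not to be considered by probation officers or parole boards. Those promises can coexist with the notes. Probation staff also see the youth use the booth, so the notes tell them little that is new.

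Part of this stands. The promises on use and effect are not contradicted. It is also correct that probation staff would know in any case, but this counts against the unqualified promise: it is untrue in more places than one. Statements about consequences do not make a statement about non-disclosure true.

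A reader might infer more: that youths, knowing probation will see their consent status, answer favourably, so that the single-arm change in self-reported DERS-16, PHQ-9 and GAD-7 is inflated. The protocol does not support this. The notes carry no answers, and no section says that youths are told of the notes. A concern about favourable answering would have to rest on probation staff administering the scales or holding the exit interview, which is a separate matter. Even then its size could not be derived from the protocol.

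A reader might also say that the protocol enters withdrawals in a probation case record. The text speaks only of verified and continuing consent in staff notes. That a withdrawal would become visible there is a reasonable inference, not a stated procedure.

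**Conclusion.** The contradiction is established by the text. Recording continuing consent in probation notes and promising that probation staff receive no information on participation cannot both be carried out, and the promise is untrue as written. It affects every participant for the whole study and needs correcting before assent and consent rely on it.

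The weight of the point rests on the truth of an assurance concerning incarcerated minors, not on bias in the results. Discouraged withdrawal is plausible but inferred. Inflated outcomes are not shown, and no figure can be put on either.

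One assumption is needed: that the promise in Consent and Assent Process is passed on to youths and parents. The forms themselves are not available here, so their wording should be checked.

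**What to change.** 1. In the Consenting text, delete *probation* from both sentences on continuing consent. Keep these records, including new information given, only in clinical or behavioral-health staff notes or in the study file, with notice to the principal investigator.
2. In the same amendment, limit the promise in Consent and Assent Process to what can be kept: participation will not be considered in, or affect, case decisions, as Confidentiality Protections and Subpart C already say, and no consent status or study responses are entered in probation notes.
3. Reconcile that promise with the supervision, oversight, assessment, exit-interview, recruitment and consent roles listed above. Where a clinical alternative is already named, use it. Two further conflicts belong here: HIPAA Waivers says that recruitment is done solely by behavioral-health staff, while Subpart C includes probation officers; and Vulnerable Populations keeps probation officers out of obtaining assent, while the Consent Process gives consent tasks to probation or clinical staff.
4. Make the assent and consent wording match.

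The first change costs almost nothing: clinical notes and notice to the investigator are already required. The rest is a short protocol amendment with matching edits to the assent script and consent form. If probation staff were expected to give assessments or hold exit interviews, that work moves to clinical staff, and the facility should confirm that they can absorb it.
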